5.1.1 Administration of Study Drugs

Preparation of infusion fluid

- Dissolve each of the 4 vials that are contained in a carton with 35 mL of 5% Dextrose or 0.9% sodium chloride solution. Upon reconstitution a total of 140 ml will be available across 4 vials.
- Remove 140 ml from a 500 mL IV container of Dextrose and replace with the 140 ml of reconstituted drug solution
- The initial loading dose is 5 mg/kg for one hour via infusion pump
- After the loading dose, 20 mg/kg/day is infused continuously via infusion pump

In the event of any significant dosing errors, the PPI and Mylan should be contacted immediately.

Since Legalon® SIL is potentially life-saving, reduction or elimination of dosing is to be avoided unless there is strong reason to think that an adverse event is due to Legalon® SIL, is clinically significant, and cannot be managed otherwise.

5.2 Drug Inventory

Legalon® SIL will be dispensed to enrolling sites from an institution/vendor designated by Mylan. Legalon SIL should not be stored above 25°C / 77°F.

The medical community will be alerted to the availability of Legalon® SIL via communication with poison control centers, mushroom organizations, and emergency room hospitals/physicians. There will be an emergency hotline number which the US physicians can call to initiate the process of obtaining Legalon® SIL.

Because amatoxin poisoning occurs episodically and randomly throughout the USA, most physicians wishing to enroll their patients on the study will not have prospective IRB approval of this protocol. The OSI will need to supply documentation of approval of this protocol from the IRB of his/her respective hospital.

5.3 Mylan will be responsible for furnishing study drug supply for distribution. Study Medication Complaints

In the event the patient has a complaint/concern during study participation regarding the supplied study medication, they should contact the site.

In the event of a complaint/concern during study participation, regarding the supplied study medication, the site should contact the sponsor. As a minimum the following information should be sent by the site as part of the complaint:

Study number: SB16A1.07

- OSI name, site address, contact number
- Subject ID.
- Date of occurrence of incident/complaint.
- Description of incident/complaint (facts).
- Confirmation if the complaint caused or resulted in a SAE? If "Yes", confirmation that the SAE has been reported.

Additional information and potentially the return of study medication may be requested by Mylan in order to investigate the complaint.

5.4 Storage, Disposition of Unused Study Drug and Drug Accountability

The Investigator, or an approved representative, e.g. pharmacist, will ensure that all investigational products are stored in a secured area under recommended storage conditions and in accordance with applicable regulatory requirements while at the investigator site.

Study drug should be stored in accordance with the drug label. Storage conditions stated in the Investigator's Brochure may be superseded by the label storage.

Temperature of storage facilities should be monitored and recorded on a daily basis using validated devices that record maximum and minimum temperatures. Should the storage facility experience any excursion of temperature outside of the labelled storage condition this must be reported immediately to Mylan or designee

The investigator must maintain adequate records documenting the receipt, use, loss, or other disposition of the study drug. Mylan will supply drug accountability forms for this study. The form must be fully completed and identify the study drug, including batch or code numbers, and account for its disposition on a subject-by-subject basis, including specific dates and quantities. The forms must be signed by the individual who dispensed the drug, and copies must be provided to Mylan or designee.

Upon completion of each patient treatment at site, the site must return all used and unused vials as well as drug accountability log and administration records redacted of all personal identifiers with subject study identifier added.

5.5 Concomitant Medications

All concomitant medications taken during the study (from signing informed consent to discontinuation of study drug) must be recorded with indication, daily dose, and start and stop dates of administration in the CRF.

Medications taken within 28 days prior to screening and prior to dosing with study medication will be documented as a prior medication. Medications taken after dosing begins with study medication will be documented as concomitant medications.

There are no prohibited medications for this study.

6 STUDY CONDUCT

6.1 OSI and Site Requirement for Study Participation

Patients will be identified as potential study subject at the medical facility to which they present with symptoms. The treating physician at the local medical facility will either reach out to a Poison Control Hotline or will call the study designated hotline directly. Upon notification of the potential subject to the Mylan designated PPI, the following actions will take place:

- The designated hotline service for the study will contact the assigned coordinator for the study and be provided with contact information for immediate follow-up. This information includes
 - Treating physician's name
 - Contact details (telephone number and email) of treating physician
 - Medical facility name and address and phone number
- The assigned study coordinator will triage the call to assure there is suspicion of amatoxin poisoning and direct the case to the PPI
- The PPI will contact the treating physician to discuss the case(s) of amatoxin poisoning to determine eligibility for treatment under the protocol and complete the PPI Eligibility Confirmation Form(s). The information on the PPI eligibility confirmation form will include:
 - Date/Time of contact
 - Name and institution of referring physician
 - Referring physician contact phone number and email
 - Number of patients in cohort
 - If patient(s) included in study:
 - Written confirmation that the criteria for inclusion have all been met : mushroom eating history, Gastrointestinal symptoms, elevated liver function tests
 - If patient(s) excluded from study.
 - Reason for exclusion must be documented.
- Upon confirmation of eligibility for the subject(s), the treating physician must immediately contact the IRB for approval of treatment according to the protocol. At the least, an email or a memo with indication of IRB approval for the subject(s)' participation in the study must be provided to the PPI/SC prior to drug shipment.
- Upon receipt of the IRB approval email/memo, the PPI will direct dispatch of the study drug to be shipped to the medical facility
- The assigned SC, in the interim, will send the following documentation to be processed by the treating physician, now the prospective On-Site Investigator (OSI),
 - FDA Form 1572
 - OSI Commitment Form
 - OSI Financial Disclosure
 - Protocol
 - Informed Consent Template
 - Case Report Forms (CRFs) and Completion Guidelines
 - SAE Form
 - Drug Accountability Form

As soon as possible after enrollment of new patient into the study but no later than 24 hours, the Primary Study Coordinator will conduct a study training teleconference with the On-Site Investigator (OSI) and his designee(s). Training will include but not limited to the review of the protocol, safety reporting, and completion of CRFs.

6.2 Screening Phase (Screening/Presentation and Pre-first Dose)

- a) Subjects eligible for study recruitment will have the nature, purpose, and risks of the study explained to them by the investigator. They will be provided with a written copy of the informed consent form (ICF) for the study and given sufficient time to consider the study's implications before deciding to participate. Subjects agreeing to participate in the study will sign the ICF and be given a duplicate copy before undergoing any screening or pre-screening (if required) procedures. Please note that due to the potential critical condition of subjects considered for this trial, informed consent may need to be obtained from the LAR or other responsible party per sites consenting policy and/or ICH GCP guidance. A unique subject identifier will be issued at the time of consent.
- b) Due to the emergent treatment requirement of the study drug, a signed informed consent from the patient may be delayed, as the patient may be incapacitated. However, until this is possible, consent from the LAR must be obtained. Documentation of the consenting process, including interim consent obtained from the LAR, must be documented in the patient's medical record. Signed consent from the patient must be obtained at the earliest time possible. A signed copy must be given to the patient/LAR as well as sent electronically to the assigned SC. The original copy should be kept in the patients' medical record along with a copy of the protocol.
- c) Once a subject enrolls in this trial the site will make every effort to retain the subject for the planned duration of the trial. In cases where the subject does not return for the post discharge Follow-up Visit or cannot be reached to reschedule the missed visit, the site should make every effort to regain contact with the subject so that they can appropriately be withdrawn from the study. All contact attempts should be documented in the subject's medical record. Should the subject continue to be unreachable, then and only then will he/she be considered to have withdrawn from the study with a primary reason of "Lost to Follow-up." For all other subjects withdrawing from the study, an alternative reason for discontinuation should be recorded in the CRF. Regardless of site plans to support and retain subjects within the trial, subjects may voluntarily withdraw from the trial for any reason and at any time.

For a subject that completes the study and all procedures it is anticipated that the duration of study would be approximately 20 days, inclusive of follow up visit.

6.2.1 Required Screening Study Procedures for Assessment and Confirmation of Eligibility for Treatment:

- Informed consent
- History

- Physical
- Vital signs
- Serum HCG in women of child bearing potential
- AST
- ALT
- Bilirubin
- PT
- INR
- BUN
- Creatinine
- Lactate
- Amylase
- Lipase
- Ammonia
- CBC with differential
- Platelet
- Glucose
- Na
- K
- Recovery of toxin (if possible)
- Baseline medical conditions
- Baseline medications

For details and timings of assessments, refer to Section 6.5.

The Protocol requires that the OSI contact the PPI for a daily telephone consultation once the patient is enrolled and for the duration of treatment with the study drug. All consultations will be documented and maintained on file by the PPI and OSI.

6.3 Treatment phase

Following receipt of study drug, if patient remains eligible for enrollment according to the protocol, treatment with Legalon® SIL should begin as soon as possible as a continuous infusion until the PT/INR have returned to the normal range set by the institution and transaminases have returned to no greater than 2 times the institutions upper limit of normal. If the laboratory tests and/or the patient clinical picture is not improving after 96 hours on treatment the PPI and OSI must specifically discuss the benefit of continued treatment. Full documentation and reason for decision to either continue or discontinue treatment must be documented in the patient's medical record as well as on the Daily Communication CRF.

Every effort should be made to ensure that the protocol required tests and procedures are completed as described. However, it is anticipated that from time to time there may be circumstances, outside of the control of the investigator that may make it unfeasible to perform the test. In these cases, the investigator or designated representative will take all steps necessary to ensure the safety and well-being of the subject. When a protocol required test cannot be performed the investigator or designated representative will document the reason for this and any corrective and preventive actions which he/she has taken to ensure that normal processes are adhered to as soon as possible. The Mylan study team will be informed of these deviations in a timely fashion.

6.3.1 Required Daily Study Assessments/Procedures While on Study Treatment

- Physical
- Vital signs
- AST
- ALT
- ALP
- Bilirubin
- PT
- INR
- BUN
- Creatinine
- Lactate
- Amylase
- Ammonia
- CBC with differential

- Platelets
- Glucose
- Na
- K
- AEs
- Concomitant medications
- Infusion of Legalon® SIL
- Other measures to eliminate residual toxin, maintain perfusion and vital signs, and prevent coagulopathy will be at the discretion of the OSI.

6.3.2 Early Termination of study drug Termination

Subjects may request termination of study drug or withdrawal from the study at any time, or be required to withdraw or terminate study drug by the investigator or sponsor for reasons as per Section 4.3.4. If study drug is terminated or the subject withdraws or is withdrawn, the reason for termination/withdrawal should be established and recorded. If a subject does not return for the follow up visit, every effort should be made to contact the subject. In any circumstance, every effort should be made to document the outcome of subject contact attempt, if possible. The investigator will contact Mylan or designee, in the event that a subject fails to complete the study or violates the protocol.

If the subject withdraws from the study and also withdraws consent for disclosure of future information, no further evaluations should be performed and no additional data should be collected. The sponsor may retain and continue to use any data collected before such withdrawal of consent.

Unless consent is withdrawn, subjects who prematurely terminate study drug will be asked to return to the clinic for the follow up visit and will have this scheduled within 10 days of stopping the study drug.

6.4 Follow-up Phase

Patients will be followed 10 days +/-2 after stopping Legalon® SIL therapy unless they failed treatment and proceeded to transplant. Follow up will consist of a physical examination and blood work to assure recovery and to assess for any AEs.

Subjects will be reminded that SAEs should be reported to the study staff up to 30 days after the last dose of study medication.

If the patient recovers from the poisoning, upon discharge from the hospital, they should be given a prescription for follow up blood work to include PT/INR and liver function studies as well as instructed to follow with their local physician for a physical exam. The OSI or designee is responsible for following up with the patient for the results of the exam and blood work.

6.4.1 Safety Testing

6.4.1.1 Adverse Event Assessment

If a subject reports any symptoms that could preclude the drug administration before starting, they will be evaluated by medical staff and necessary measurements will be performed. The OSI will be notified before dosing to determine the course of action.

Findings from screening procedures, e.g., laboratory tests or physical examinations will be recorded as medical history. Clinically significant changes following completion of the screening procedures will be recorded as adverse events.

Subjects will be routinely queried in regards to the presence or absence of adverse events using open ended questions. The treating medical staff will provide documentation of any adverse events in the subject’s CRF. The adverse event source documentation will minimally include the following information: date and time of assessment, description of the adverse event, date/time of onset, date/time of resolution if applicable, and identification of the staff member collecting the information.

There are no adverse events of special interest for this study.

6.4.1.2 Laboratory Safety

6.4.1.2.1 Blood Volume

Total blood volume collected per patient for this study will vary between treating institutions. The blood assessments required per the protocol approximate the sampling that would be conducted as standard of care for patients suffering from the effects of amatoxin poisoning and as such do not pose any additional risk to the patient. The following safety laboratory tests will be performed at times defined in the study schedules in Sections 1 and 6.

Table 2 Laboratory Safety Tests

| Hematology | Chemistry | Other |
|-------------------------|-----------------------|---------------------------------------------------------------------|
| Hemoglobin | Urea and Creatinine | Serum Pregnancy in women of childbearing potential (screening only) |
| Hematocrit | Glucose (non-fasting) | |
| RBC count | Sodium | |
| Platelet count | Potassium | |
| WBC count | AST, ALT | |
| Total neutrophils (Abs) | Total Bilirubin | |
| Eosinophils (Abs) | Alkaline phosphatase | |
| Monocytes (Abs) | Lactate | |
| Basophils (Abs) | Lipase | |
| Lymphocytes (Abs) | Amylase | |
| | Ammonia | |

Hematology and chemistry will be analyzed by the local laboratory.

Any clinically significant findings in laboratory safety data following completion of screening should be recorded as an AE. Determination of clinical significance and seriousness will be based on the Investigator's medical judgment.

6.4.1.3 Blood Pressure and Pulse Rate

Blood pressure and pulse rate will be measured at times specified in Sections 1 and 6. Additional collection times, or changes to collection times of blood pressure and pulse rate will be permitted, as necessary, to ensure appropriate collection of safety data.

Any clinically significant changes in blood pressure and pulse rate following completion of screening should be recorded as an AE. Determination of clinical significance and seriousness will be based on the OSI's medical judgment.

6.4.1.4 General Physical Examination

At screening, general physical examination will be performed which consists of an examination of the abdomen, cardiovascular system, lungs, lymph nodes, musculoskeletal and neurological systems, skin, extremities, head, ears, eyes, nose, and thyroid gland by trained medical personnel at the site.

At screening, any clinically significant abnormality should be recorded as a preexisting condition in the subject's medical history. At the end of the study, any new clinically significant findings/abnormalities that meet the definition of an adverse event must also be recorded and documented as an adverse event.

Height and weight will be assessed at screening. Physical examination results will not be recorded in the CRFs, but any clinically significant finding at Screening should be recorded under medical history and changes between Screening and subsequent examinations should be recorded as an AE. Determination of clinical significance and seriousness will be based on the OSI's medical judgment.

7 STATISTICAL ANALYSIS

7.1 Sample Size Calculations

The overall mortality rate for Legalon® SIL treated patients, regardless of the severity of liver damage, is less than 10%. This represents more than a 50% reduction in the reported mortality rate before Legalon® SIL was available. For ethical and practical reasons there are no controlled clinical studies available for any amatoxin treatments but observational studies and case reports describe successful treatment with intravenous silibinin (Legalon® SIL).

A total of 139 enrolled patients is considered sufficient to show the effect of the Legalon® SIL in preventing liver transplantation, and/or death resulting from amatoxin poisoning. Using the large sample normal approximation, a sample size of 139, provides a two-sided 95% confidence interval for proportion of patients not meeting the outcome of interest (liver transplantation, and/or death) within a half width of 5% from the observed proportion at an expected proportion of 90%.

Published Clinical Experience with Legalon® SIL

Between 1982 and 2008, mostly single cases were published by various authors (Table 7.1). Overall, out of these 1,136 reported patients treated with Legalon® SIL as monotherapy or in combination with mostly penicillin G, 1,064 patients (94%) survived. It was further reported that the severity of liver damage correlated with the time interval between mushroom intake and commencement of silibinin treatment. If silibinin was given within 48 hours after intoxication, a light or medium hepatic injury was expected. When silibinin treatment was delayed by more than 48 hours, then a severe clinical course with coagulation disorders and liver coma was more likely.

Table 3 Summary of Clinical Experience with Legalon® SIL in Amanitin Poisoning

| Reference | Treatment Regimen | No. of Patients | |
|-------------------------------------------------|-------------------|-----------------|----------|
| | | Treated | Survived |
| Lorenz et al. , 1983 (unpublished) | PE + SIL | 201 | 181 |
| Streng-Hesse et al. , 1996 (unpublished) | PE + SIL | 154 | 139 |
| Floersheim et al. , 1982 [29] | PE + SIL | 16 | 16 |
| Hruby 1983 [30] | PE + SIL | 15 | 14 |
| Marugg and Reutter 1985 [33] | PE + SIL | 12 | 11 |
| Smetana et al. , 1986 [34] | PE + SIL | 2 | 2 |
| Schenke et al. , 1987 [35] | SIL | 2 | 2 |
| Hruby 1987 [36] | SIL | 17 | 16 |
| | PE + SIL | 37 | 34 |
| | TH + SIL | 1 | 1 |
| | PE + TH + SIL | 15 | 15 |
| Kelbel and Weilemann 1989 [37] | PE + SIL | 5 | 4 |
| Nagy et al. , 1994 [38] | PE + SIL | 4 | 3 |
| Kleist-Retzow et al. , 1995 [39] | PE + SIL | 2 | 2 |
| Molling et al. , 1995 [40] | PE + SIL | 2 | 2 |
| Carducci et al. , 1996 [41] | PE + SIL | 4 | 4 |
| Alves et al. , 2001 [42] | PE + SIL | 4 | 4 |
| Boyer et al. , 2001 [43] | NAC + SIL | 1 | 1 |
| Enjalbert et al. , 2002 [28] | SIL or PE+SIL | 624 | 589 |
| Ganzert et al. , 2008 [31] | SIL or PE+SIL | 367 | 339 |
| Mitchell and Olson 2008 [32] | PE+NAC+SIL | 6 | 5 |
| Total | | 1,491 | 1,384 |

PE=penicillin, SIL=Legalon® SIL, NAC=N-acetylcysteine, TH=thioctic acid.

Based on the available clinical data (unpublished and published), from a total of 1,491 documented Amanita-poisoned patients treated with Legalon® SIL 1,384 survived, resulting in a survival rate of 93% (1a).

7.2 Analysis Set Definitions

The following analysis sets will be used for the statistical analyses:

Full Analysis Set (FAS): Full Analysis Set includes all treatment allocated subjects with least one post baseline evaluable efficacy assessment.

Safety Analysis Set (SAF): Safety Analysis Set includes all subjects who receive the study treatment.

Per-Protocol Set (PPS): Per-Protocol Set includes all subjects who receive study treatment, have evaluable efficacy assessment and have no major protocol deviations. A major protocol violation is defined as a protocol deviation that is considered to have an impact on the efficacy results. A list of possible major protocol deviations will be identified and documented in the SAP and the subjects having major protocol deviation will be finalized prior to the data base lock.

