4.3.4 Criteria for study drug termination, withdrawal from the study and study termination

Subjects will be free to request termination of study drug or withdrawal from the study at any time for any reason.

Subjects must be withdrawn from the study prior to initiating treatment under the following circumstances:

- Laboratory values indicative of recovery prior to the start of Legalon® SIL

A subject must terminate study drug for safety reasons under the following circumstances:

- Development of a SAEs that is deemed attributable to Legalon® SIL by the OSI

A subject may be required to terminate study drug for other reasons including the following:

- Patients in whom, after 96 hours of starting treatment there is no significant improvement in the PT/INR and transaminases, termination of treatment may occur following consultation between the OSI and PPI.
- If it is in the subject's best interest based on decision of the OSI or his/her Sub-Investigator e.g. due to occurrence of an AE and/or other findings considered to present a safety concern to continued dosing with study drug.
- Despite education/reinforcement, the subject shows persistent inadequate compliance with required procedures, potentially compromising safety monitoring while on study drug.

Unless consent is withdrawn, subjects who prematurely terminate study drug and are discharged from the hospital, will have PT/INR, liver transaminases collected by local lab and have a physical examination performed by local physician 10 days post last dose of study drug. The OSI is responsible for obtaining the results of these procedures from the patient.

The Principal Investigator and/or Mylan reserves the right to terminate the study for any reason.

The study will be terminated early if there are significant safety concerns.

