7.3 Primary Endpoint

The primary endpoint is the proportion of patients treated with Legalon® SIL that do not exhibit morbidity (liver transplantation,) and/or mortality (death) at the end of treatment period (96 hours).

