7.5.3 Analysis of Primary Endpoint

The primary objective of the study is to compute the survival of the patients without liver transplantation, renal failure or death during the treatment period of 96 hours. The number and proportion of patients surviving without liver transplantation, renal failure and/or death at the end of treatment period will be computed, 95% CI for the proportion of patients surviving without liver transplantation, renal failure and/or death will be computed based on Newcombe-Wilson score method.

The analysis of primary endpoint will be performed based on Full Analysis Set.

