7.6 Interim Analyses

Interim Clinical Study Report summarizes the data related to the first 50 patients of the 54 recruited, as of December, 2012 into this study with protocol No. SB16A1.07, entitled "Prevention and Treatment of Amatoxin Induced Hepatic Failure with Intravenous Silibinin (Legalon® SIL): An Open Multicenter Clinical Trial", which was originally submitted to the FDA on 9 July 2009 under IND 105,960 and is being conducted in US investigational sites. Study Objectives and Endpoints: This study aims to assess the efficacy and safety of Legalon® SIL in the prevention of severe morbidity (defined as liver transplant) and death in amatoxin poisoned patients. The primary endpoint is the proportion of enrolled patients without liver transplant or death. Secondary assessments include AST, ALT, bilirubin, PT/INR, and creatinine as indicators of liver and renal function, adverse events and vital signs.

Design: Multicenter, open, uncontrolled study.

Study Population: Patients with a clinical diagnosis of amatoxin poisoning based on history, gastrointestinal symptoms, elevated liver enzymes.

Results: 42 of the 50 poisoned patients (84.0%; 95% CI 70.9% to 92.8%) were discharged home from the hospital with complete recovery. Conversely, 8 of the 50 patients (16%) had a severe morbidity, resulting in 5 deaths and 3 liver transplants. The negative outcome of these 8 patients was due to the progression of the liver and renal failure as a consequence of Amatoxin intoxication in the absence of an adequate aggressive hydration to preserve renal function and when treatment with Legalon® SIL was instituted started >96 hours after poisoning.

A total of 11 patients (22.0%) experienced 20 Adverse Events (AEs) during the course of the clinical trial, 11 of which were Serious Adverse Events (SAEs). All SAEs were regarded as severe AEs by the on-site investigator (OSI) and all of them were considered not related to Legalon® SIL treatment. Indeed, they were all signs of the severe amatoxin intoxication, responsible for severe liver failure leading these patients to die or to be liver transplanted.

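### The primary analysis set requires a post-baseline assessment, so a treated patient who dies or is transplanted very early can fall out of the denominator of a death/transplant endpoint

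*Combined protocol and SAP*

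**What the plan says.** Section 7.3 sets the population of the endpoint: "The primary endpoint is the proportion of patients treated with Legalon® SIL that do not exhibit morbidity", where morbidity means liver transplantation, together with freedom from death, judged at 96 hours. The population is those treated.

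Section 7.5.3 then states: "The analysis of primary endpoint will be performed based on Full Analysis Set". Section 7.2 defines that set: "Full Analysis Set includes all treatment allocated subjects with least one post baseline evaluable efficacy assessment". The same section defines an all-treated set under another name: "Safety Analysis Set includes all subjects who receive the study treatment". Section 7.7 uses that set for safety only.

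The sensitivity analyses in section 7.5.4 use the Full Analysis Set and the Per-Protocol Set. The Per-Protocol Set also requires an evaluable efficacy assessment. Section 7.5.7 puts the secondary endpoints on the Full Analysis Set. Section 7.5.5 says that missing data will in general not be imputed.

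The sample size is written in terms of enrolment. Section 7.1 says: "A total of 139 enrolled patients is considered sufficient". Section 4.3.4 provides for some subjects to leave before dosing: "Subjects must be withdrawn from the study prior to initiating treatment under the following circumstances"; the circumstance listed is laboratory evidence of recovery.

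**The concern.** When the endpoint is death or transplant, any treated patient whose vital and transplant status at 96 hours is known has an evaluable outcome. A further requirement for a post-baseline assessment adds no information about that outcome. It can only remove people from the denominator.

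The people most exposed to removal are those who fail before anything is measured after the first dose. All of them are failures, so losing any of them moves the result one way, upwards. The trial has no control arm, so the observed proportion is the efficacy evidence, and sections 2.2 and 7.1 set it beside historical mortality. A small, one-directional distortion in the denominator therefore matters more than it would in a randomised comparison.

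Two terms that decide membership are left open. Being allocated to treatment has no operational meaning in a trial that, by section 4.3.3, does not randomise. The text also never defines an evaluable efficacy assessment, and so does not say whether a recorded death is one.

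**Working it through.** **1. The plan's own figure.** Inputs from section 7.1: two-sided 95% confidence, expected proportion 0.90, half-width 0.05, normal approximation.

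n = z² p(1 − p) / h² = 1.96² × 0.90 × 0.10 / 0.05² = 138.29, rounded up to 139.

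Half-width at 139: 1.96 × √(0.09 / 139) = 4.99 points. The sample size reproduces, and the arithmetic is sound.

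**2. Who is in each set.** Setting the sections side by side:

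| Set or count | Membership rule | Used for |
|---|---|---|
| Endpoint population (7.3) | treated | definition only |
| Full Analysis Set (7.2) | allocated to treatment, plus a post-baseline evaluable assessment | primary, sensitivity and secondary efficacy |
| Per-Protocol Set (7.2) | treated, evaluable assessment, no major deviation | sensitivity |
| Safety Analysis Set (7.2) | treated | safety |
| 139 (7.1) | enrolled | precision |

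No efficacy analysis is assigned to the only set whose rule matches the endpoint population.

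**3. How long the exposure lasts.** The schedule in section 1 puts the first post-dose laboratory tests at 6 hours, plus or minus 1. If tests are done on time, only a death or transplant in roughly the first 5 to 7 hours is at risk of exclusion. Section 6.3 accepts that required tests may sometimes not be feasible, which would lengthen that interval for individual patients.

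**4. Effect of dropping early failures.** The documents give no count of such patients, so the numbers dropped, k, are assumptions. Take 139 treated and 14 failures, hence 125 successes, close to the planned 90%. Success rate = 125 / (139 − k), with the Wilson score interval named in section 7.5.3:

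| k dropped (assumed) | Rate | 95% interval |
|---|---|---|
| 0 | 125/139 = 89.9% | 83.8% to 93.9% |
| 1 | 125/138 = 90.6% | 84.5% to 94.4% |
| 3 | 125/136 = 91.9% | 86.1% to 95.4% |

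Each dropped failure adds about 0.7 points (90.6 − 89.9; (91.9 − 89.9) / 3).

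**5. What the interim data can and cannot add.** Section 7.6 reports 42 successes in 50 (84.0%), with 5 deaths and 3 transplants. It does not give the time from first dose to failure, so the number who would have missed a post-dose assessment cannot be derived from it. It cannot serve as an estimate of k.

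**6. Precision.** The 4.99-point half-width holds only if all 139 are analysed. If 5% of the 139 enrolled (assumed) were not analysed, n is about 132 and the half-width is 1.96 × √(0.09 / 132) = 5.12 points. At 10% (assumed), n is about 125 and it is 5.26 points. These are small changes. They show that the meaning of 139 should be stated, not that the trial is too small.

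**The case against.** The strongest reply is that the text is silent and does not exclude anyone who dies. A sensible analyst would treat a recorded death as an evaluable assessment of an endpoint made up of death and transplant. On that reading no early failure is lost. Even on the other reading the window is a few hours, and every figure for dropped patients is hypothetical. Section 7.5 also leaves detail to a statistical analysis plan, which could settle the wording. All of this stands, and it limits the size of the point. It does not remove it: the written rule leaves the matter to judgement in an open-label trial, and no planned efficacy analysis would show which reading was used.

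A reader might infer more than the documents support, in three ways.

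- **That patients enrol before ethics approval and are lost while waiting for drug.** Section 8.5.1 requires approval documents to reach the sponsor before enrolment, and section 6.1 requires an indication of approval before drug is shipped. Undosed subjects are still possible: identifiers are issued at consent (6.2), and eligibility is rechecked when drug arrives (6.3).
- **That leaving out undosed patients inflates the rate.** Their exclusion agrees with an endpoint defined among the treated. The direction of any effect is also unknown, because the pre-dose withdrawal that section 4.3.4 requires is for recovery and so removes likely successes.
- **That the interim endpoint shows a conflicting current denominator.** Section 7.6 does say "The primary endpoint is the proportion of enrolled patients without liver transplant or death", but it summarises an earlier report, and it shows no undosed patient among the 50.

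**Conclusion.** The point holds in a limited form. The primary analysis set carries a condition that the endpoint definition does not, and for this endpoint the condition can only remove treated patients. If it removes early failures, the bias is upward, by about 0.7 points per patient near 90% success. On the assumed illustration this is 89.9% to 90.6% for one patient, or to 91.9% for three.

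The conclusion rests on two assumptions: that a death or transplant without a post-dose assessment might be read as not evaluable, and that at least one such patient occurs. The documents settle neither, and the 6-hourly schedule suggests few cases. The change is still worth making before database lock, because the correct set already exists in the plan and the change costs almost nothing. The mismatch between enrolled and treated is a matter of wording and minor precision, not evidence of a biased analysis.

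**What to change.** - In sections 7.2 and 7.5.3, make the primary efficacy set all subjects who receive any amount of study drug, which is the existing Safety Analysis Set. Drop the references to allocation and to a post-baseline assessment.
- State that death or liver transplantation after the first dose and within the protocol's endpoint window is an evaluable failure, whether or not any other assessment was made. Counting events at any time after first dose would replace the 96-hour window of section 7.3. That is a change of endpoint, which section 7.5 would route through a protocol amendment, and this fix does not need it.
- State how a treated patient with unknown outcome at the end of the window is counted.
- In section 7.1, say whether the 139 are enrolled or treated. If enrolled, restate the half-width for the expected undosed fraction.
- List enrolled but undosed subjects and their known outcomes separately and descriptively, with withdrawals for recovery identified.

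The cost is wording and one small listing. Adverse events are collected from consent (9.1.1), but section 8.3 requires case report forms only for subjects who receive drug, so the listing may need a short outcome record for undosed subjects. The sample size does not change if all 139 are dosed. The reported success rate may be slightly lower.
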